**Outcomes: Primary Aim:** To demonstrate that IN ketorolac is non-inferior to IV ketorolac in reducing pain in children with acute migraine headaches, we will compare the mean decrease in pain score of both study groups at 60 minutes after administration of the study drug to each other. The outcome we will use to measure this decrease in pain will be the Faces Pain Scale – Revised (FPS-R). The FPS-R is a 10 point pain scale that has been validated for the use in children greater than 4 years of age in the ED; is one of the self-report measures of pain recommended for research in children; and is commonly used as the primary outcome in ED research.(56,57) IN ketorolac will be considered non-inferior to IV ketorolac if the difference between the mean decreases in pain score of both groups is less than a clinically meaningful difference in pain. The minimum clinically meaningful difference in pain in children when using the FPSR has been shown to be 2 out of 10, and is consistent across all categories of age, sex, ethnicity, and primary language; (58) therefore, the non-inferiority margin (delta) will be set at 2/10. In addition to the FPS-R, we will also assess pain using a descriptive ordinal scale frequently used in headache research.(59) Using this scale, we will ask the patient to describe their headache pain as severe, moderate, mild, or none. We will also use the verbal numeric rating scale (vNRS), which involves asking the patient how much pain they have on a scale from zero to ten. We selected the reduction in pain, rather than pain freedom as recommended by the IHS guidelines, as pain freedom is very seldom achieved in the ED, with only approximately 20% of patients reportedly being pain free upon discharge. (59-61) Prior comparative trials of abortive migraine and headache therapies in the ED have similarly shown that as few as 15% of adults and 7% of children achieve headache freedom after treatment, but greater than 60% experience headache relief.(40,62) As a result, pain freedom from migraine or headaches has been infrequently used as the primary outcome for studies in the ED setting; instead, degree of pain relief has been used.(37-40,63-66) Additionally, we chose the one hour end point based on the IHS recommendations that a time point earlier than two hours should be considered for parenteral study medications (which would apply to both IV and IN routes).(59)

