Secondary Aim: To determine if there is a difference in time to achieve a clinically significant reduction in pain after receiving IN ketorolac compared to IV ketorolac, we will use the outcome of time (in minutes) and compare, as appropriate, the mean or median time it takes after administration of study drug in each group to achieve a minimum clinically significant difference in pain (i.e. 2/10 on the FPS-R).

Note that a prior iteration of the protocol stated that this secondary aim was to determine if IN ketorolac was non-inferior to IV ketorolac, with a non-inferiority margin for this aim of 10 minutes. This secondary aim was changed prior to starting patient enrollment (i.e. no patients were enrolled yet) because the number of pain assessments was decreased from assessments at 10, 20, 30, 40, 50, 60, and 120 minutes to 10, 30, 60, and 120 minutes for feasibility reasons. Since we would then no longer be able to assess change in pain score in 10 minute increments, it would not have been possible to accurately assess for non-inferiority based on a non-inferiority margin of 10 minutes. Therefore, the aim was changed to as is currently stated.

Additional efficacy outcomes will include those that are ED-based, and those assessed at a 24- hour follow up:

- i) ED-based outcomes: 1) Receipt of rescue medications at any time during the ED visit; 2) Headache relief in the ED, defined as change within 2 hours of the patient's description of headache from severe or moderate to either mild or none, on the severe/moderate/mild/none pain scale, without the use of rescue medications; 3) Headache freedom in the ED, defined as achieving a headache level of none within 2 hours without the use of rescue medications; and 4) Percentage improvement in pain score between baseline and one hour, defined as (baseline pain score – one hour pain score)/baseline pain score.

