- ii) 24-hour follow up outcomes: 1) The patient's overall assessment of efficacy and tolerability, expressed as a dichotomous response to the question, "The next time you come to the emergency department with a headache or migraine, do you want to be given the same medication (that is, the medicine you received first)?"; 2) Sustained headache freedom, defined as achieving a level of none on the severe/moderate/mild/none within 2 hours of medication administration and maintaining this level continuously for 24 hours without the use of rescue medications; 3) Sustained headache relief, defined as change within 2 hours of the patient's description of headache from severe or moderate to either mild or none without the use of rescue medication, and maintaining this level of relief continuously for 24 hours without the use of rescue medications; and 4) Use of rescue medications, if any, during the 24-hour period after initial medication administration after discharge from the emergency department (if yes, which one).

Functional outcomes will be assessed during their ED stay and at the 24-hour follow up. We will use a question standard in headache research, but modified to suit the pediatric population:

"Do you think you could do all of your usual daily activities? Usual daily activities can include things like going to school, doing your homework, doing your chores, playing games (including video games), reading, or playing sports." Available responses will include: a) I think I could do everything I usually do without any problems (or difficulty). b) I think it would be a little bit hard (or difficult) to do everything that I usually do. c) I think it would be very hard (or difficult) to do everything that I usually do, and I could only do the easiest things. d) I don't think I could do any of the things I usually do at all. (59) Safety outcomes will be assessed at the 1- and 2-hour assessments and the 24-hour follow up. We will ask the patient whether they have experienced any new or different symptoms. If they answer in the affirmative, their symptoms will be elicited with an open-ended question.

The procedure for breaking the blind in this study is as follows: In the event of a serious adverse event (defined as a medical occurrence that results in death, is life-threatening, requires inpatient hospitalization, results in

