persistent of significant disability/incapacity), not only will this event be reported to the IRB, but it will be reported to the study DSMB within 7 days of the event occurrence for consideration of unblinding. The DSMB will decide whether or not to break the blind based on whether or not they deem it necessary for the care of the subjects or conduct of the study.

We will be conducting a retrospective medical record review to identify a missed eligible population (i.e. patients who are eligible, but are not screened or enrolled). The reason for this review is to ensure scientific credibility by showing that we are not enrolling a biased sample of children. This review is necessary because as patients come to the emergency department 24/7, it is inevitable that some eligible patients will be missed. This population of missed eligible patients will not be subjected to study procedures or interventions. The data points collected for these patients will be retrieved from existing medical records and are both limited and specific. These data points include: age; sex; initial pain score; medications received in the emergency department; and disposition (e.g. home, admission). No personal identifiers will be collected for this population of missed eligible patients. Each of these patients will be de-identified and assigned a unique subject number at the point of data entry. There will be no key that will link the subject number to the patient.

**Study Drugs and Devices:** Ketorolac is a commonly administered NSAID that is used to treat pain in both adults and children, for conditions ranging from headaches, back pain, kidney stones, and fractures. It is typically administered by the IV or IM route, but has been studied when administered IN, mainly in adults, with both its clinical effects and pharmacokinetic properties well described. Ketorolac is commonly administered as part of clinical care for pediatric emergency department patients, and is stored in the usual pharmacy-controlled areas in the pediatric emergency department. The ketorolac which will be administered is the same formulation, and patients being enrolled in this study have already been determined by their treating physician to require ketorolac as part of their usual care.

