To demonstrate the appropriateness of using the Irma criteria for diagnosing migraines in children in the ED, one prior study has shown that the original iteration of the Irma criteria is almost twice as sensitive as the ICHD-II criteria with annotation for children for diagnosing migraine headaches in children in the ED setting.(43) Although the original iteration of the Irma criteria requires fulfillment of four criteria, decreasing the requirement to three (i.e. the modified Irma criteria) increased the sensitivity to 95%.(43) We have chosen to use the modified version so that it would be possible to study a more generalizable population of children who present to the ED with likely migraine headaches.

Per the modified Irma criteria, children in our study will be eligible if they have a headache that fulfills at least three of the six following criteria: i) moderate to severe episode of impaired daily activities; ii) focal localization of headache (focal meaning unilateral, bifrontal, bitemporal, or biparietal); iii) pulsatile description; iv) nausea or vomiting or abdominal pain; v) photophobia or phonophobia or avoidance of light and noise; and vi) symptoms increasing with activity or resolving by rest. Additionally, the eligible child must have a headache of moderate to severe pain (defined as 4/10 on the validated Faces Pain Scale – Revised (FPS-R) pain scale) and require any IV medication for treatment of their migraine headache (e.g. ketorolac, metoclopramide, prochlorperazine), as decided by their attending ED physician. We will enroll patients with a headache duration between 1 and 168 hours (i.e. 7 days).

We will exclude patients for any of the following: any contraindication to receiving ketorolac (e.g. known allergy, known peptic ulcer disease, gastrointestinal bleeding, renal impairment, known bleeding disorders); receipt of an NSAID (e.g. ibuprofen) within previous six hours; presence of intranasal obstruction (e.g. mucous or blood) that cannot be readily cleared using suction or nose blowing; inability to speak English or Spanish; unable to complete self-report measures of pain or questionnaires (e.g. developmental delay, neurologic impairment); known underlying hepatic impairment; critical illness; and frequent use of drugs for headache (defined as regular intake of analgesics for acute headaches on more than 10 days per month).

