### **Statistical Procedures:**

We will enroll 80 children (40 in each group) ages 8 to 18 years. We based our sample size on the ability to demonstrate non-inferiority between the IN and IV ketorolac groups' ability to reduce pain. It has been shown that a reduction of 2 on the FPS-R score is the minimum clinically significant difference in pain in children. Therefore, our predetermined margin of non-inferiority is 2. In order to be conservative for the sample size calculation, we based the calculation on a margin of 10% less than our predetermined margin of non-inferiority of 2. The resulting sample size of 80 children, therefore, is based on a margin of 1.8 on the FPS-R pain scale. Using a standard deviation of 2.725 (again, selected using conservative assumptions), a sample size of 40 patients per group provides 90% power to detect non-inferiority using a one-sided two sample t-test with an alpha of 0.05.

We will conduct an intention to treat analysis for all enrolled randomized subjects. We will conduct a one-sided t-test to evaluate the difference between the mean decreases in pain score of the two study groups (primary outcome). The difference between groups, with its 95% CI, will be compared to the pre-determined non-inferiority margin (i.e. 2/10) to establish whether IN ketorolac is noninferior to IV ketorolac. For our secondary outcome (time to clinically significant reduction in pain), we will also compare groups using a two-sample one-

sided t-test. Similar to the analysis for the primary outcome, the difference between groups in the time to clinically significant reduction in pain, with its 95% CI, will be compared to the pre-determined non-inferiority margin of 10 minutes. A Kaplan-Meier distribution analysis will also be used to compare the time to meaningful pain relief in the two treatment groups. For other secondary outcomes, we will compare groups using standard bivariate analyses for categorical and continuous variables and a table describing adverse events by treatment will be reported.

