### **Potential Risks:**

There are no risks in addition to the usual risks associated with receiving ketorolac for analgesia. There is a chance that a patient may not experience the same degree of pain relief that they may have experienced if they had received IV ketorolac. However, patients will have their pain assessed as per usual standard care, and can receive any additional required analgesics at any point in time if their pain relief is inadequate. The procedures involved in this study do not increase the risk for adverse events normally associated with receiving ketorolac.

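### Rescue analgesia is allowed before the 60-minute pain score that decides non-inferiority, and the primary analysis has no rule for it

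*Combined protocol and SAP*

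**What the plan says.** The primary comparison, under Outcomes, is to "compare the mean decrease in pain score of both study groups at 60 minutes after administration of the study drug", measured on the FPS-R. Statistical Procedures adds: "We will conduct an intention to treat analysis for all enrolled randomized subjects". It specifies a one-sided t-test and a margin of 2 points. Neither section mentions other drugs given before the score, and no per-protocol or sensitivity analysis is listed.

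Potential Risks states that children "can receive any additional required analgesics at any point in time if their pain relief is inadequate". No section sets a minimum wait. The 24-hour question about treatment preference refers to "the medicine you received first", so the authors expected some children to receive further drugs.

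Rescue is handled in the secondary outcomes. One ED outcome is "Receipt of rescue medications at any time during the ED visit". Headache freedom in the ED is defined as "achieving a headache level of none within 2 hours without the use of rescue medications". Headache relief and the two sustained 24-hour outcomes carry a similar condition.

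On entry, Study Subjects requires that the child "require any IV medication for treatment of their migraine headache (e.g. ketorolac, metoclopramide, prochlorperazine", as judged by the attending physician. Study Drugs and Devices says instead that "patients being enrolled in this study have already been determined by their treating physician to require ketorolac as part of their usual care".

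**The concern.** In a non-inferiority trial, anything that narrows the difference between arms helps the claim. Rescue is triggered by poor relief. If IN ketorolac is the weaker treatment, more IN children can be expected to need rescue before 60 minutes, and their scores then include the benefit of the second drug. Under intention to treat those scores would count as they stand. The planned test would compare IN ketorolac plus more rescue with IV ketorolac plus less rescue, while the stated aim is to compare the two routes.

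The plan already separates relief with rescue from relief without it, but only for secondary outcomes. The rescue outcome covers the whole ED visit, so as defined it does not show how much rescue came before the decisive score.

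The two entry statements matter because they leave open what happens to the drug the attending had in mind. If every child was judged to need ketorolac, study drug simply takes its place. If some were judged to need a different drug, the plan should say whether study drug replaces it.

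**Working it through.** **Inputs from Statistical Procedures:** SD 2.725; 40 per arm; margin 2 for the conclusion and 1.8 for the sample size; one-sided alpha 0.05; a 95% CI compared with the margin.

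**Assumptions, not in the documents:** true IN deficit of 2 points without rescue (the margin itself); mean IV decrease 3.5; rescue adds 2 points; the early-rescue rates below.

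**1. The plan's own figure.** SE = 2.725 × √(2/40) = 0.609. At margin 1.8 with no true difference, 1.8/0.609 = 2.95. Power is 0.905 by the normal approximation and 0.900 by the noncentral t with 78 df. The stated 90% with 40 per group reproduces.

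**2. No rescue.** With a true deficit of 2 and margin 2, the chance of a false non-inferiority claim is 5.0%.

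**3. Unequal rescue, by formula.** If rescue adds g points to the decrease, the expected difference is 2 − g × (IN rate − IV rate).
- 13% against 5%, g = 2: 2 − 2 × 0.08 = 1.84. The shift is 0.16/0.609 = 0.26 SE and the false-claim rate is 8.3%.
- 26% against 11%, g = 2: 2 − 2 × 0.15 = 1.70. The shift is 0.30/0.609 = 0.49 SE and the rate is 12.4%.

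Read from the 95% CI (one-sided 0.025, nominal 2.5%), these become 4.5% and 7.0%.

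**4. Rescue triggered by poor relief, by simulation.** These rates arise if 30% or 60% of children whose unrescued decrease is below 1 point are rescued. The share below 1 is Φ((1 − 1.5)/2.725) = 0.43 in the IN arm and Φ((1 − 3.5)/2.725) = 0.18 in the IV arm. Multiplying by 0.3 gives 13% and 5%; by 0.6, 26% and 11%. The planned test then claims non-inferiority falsely in about 8% and 14% of trials. The second figure exceeds the formula because rescue goes to the worst responders and narrows the spread of scores.

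**5. Other assumed values, by the formula in step 3 (one-sided 0.05).**

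| Early rescue, IN against IV | Adds 1 point | Adds 2 points | Adds 3 points |
|---|---|---|---|
| 10% against 10% | 5.0% | 5.0% | 5.0% |
| 20% against 10% | 6.9% | 9.4% | 12.4% |
| 30% against 10% | 9.4% | 16.0% | 25.2% |

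Equal use with an additive benefit gives no bias.

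**6. Using the score just before rescue.** In the two scenarios of step 4, putting the pre-rescue score in place of the 60-minute score brings the false-claim rate back to about 5%. This assumes that the pre-rescue score stands in for what the child would have reported at 60 minutes.

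**7. Where that analysis fails.** If a second drug is given alongside study drug, the last score before it is the baseline, so the recorded decrease is 0 in both arms. With equal use of 10%, 25% or 50%, the expected difference is 2 × (1 − share) = 1.8, 1.5 or 1.0, and this analysis claims non-inferiority falsely in about 9%, 21% or 60% of trials.

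**The case against.** The strongest reply is that intention to treat answers the question: every score counts, whatever else was given. Treatment groups are concealed from patients and pain assessors, which limits deliberate unequal use. Rescue is compared between arms, so a large overall imbalance would show. The data collection form is not in the documents, so drug names and times may already be recorded. All of this stands. But intention to treat mainly settles who is analysed; the plan never says what a 60-minute score after rescue is meant to represent. Blinding does not stop poorer relief from prompting more rescue, and a whole-visit count does not locate it before or after the primary score.

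A reader might go further and infer that the entry criterion brings in children who will receive metoclopramide or prochlorperazine together with study drug. The documents do not support that. Those drugs appear in a list of examples with ketorolac first, which can be read as a threshold for needing IV treatment. Study Drugs and Devices says that ketorolac was judged necessary. The 24-hour question suggests study drug first and other drugs later, and Potential Risks ties additional analgesics to inadequate relief. Co-treatment from time zero is not described anywhere.

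A reader might also infer a gross inflation of the error rate. If half of both arms received a second drug that abolished the route difference in those children, the false-claim rate would reach 47% (35% on the 95% CI). Nothing in the documents points to use on that scale or to an effect that complete.

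Finally, a compulsory 60-minute hold on other migraine drugs would not be a free remedy. Nausea or vomiting is among the qualifying features, and metoclopramide and prochlorperazine are also antiemetics, so a hold is a clinical trade-off.

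**Conclusion.** The point holds in this form: rescue is permitted before the primary score, the primary analysis has no stated way of handling it, and following the plan exactly can bias the comparison toward non-inferiority. At one-sided 0.05, the false-claim rate rises from 5% to about 8% for assumed early rescue of 13% IN against 5% IV, and to about 14% for 26% against 11%. This rests on a true deficit of 2, a mean IV decrease of 3.5 and a rescue benefit of 2 points. The bias is conditional: it needs more early rescue in the IN arm, or a second drug that blunts the route difference, and it is nil when use is equal and the benefit additive. Actual early-use rates are unknown. The two entry statements also disagree and should be reconciled. This is a cheap improvement; it does not show that the design is unsound.

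**What to change.** - In Study Procedures, state that study drug is given first, in place of the IV migraine drug the attending had planned. Before the 60-minute score, other migraine drugs are given only as rescue for inadequate relief or when clinically needed, with no mandatory hold.
- Record the name and clock time of any such drug, and take an FPS-R score just before it.
- Keep the intention-to-treat t-test as the primary analysis. Pre-specify a sensitivity analysis that uses the last FPS-R score before the other drug for children given one before 60 minutes, and a supportive analysis in children given none. Report counts by arm.
- Interpret a non-inferiority claim with caution if the sensitivity analysis disagrees. Do not make it a formal gate, because it does not correct for a second drug given alongside study drug at equal rates (step 7 of the working). The analysis in unrescued children selects on an event after randomisation, so it is supportive only.
- Align the sentence in Study Drugs and Devices with the criterion in Study Subjects.

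The cost is one extra pain score before rescue, two data fields and two analyses. The sample size stays at 80. If 10%, 25% or 50% of children drop out of the supportive analysis, 36, 30 or 20 per arm remain, with power 0.925, 0.878 or 0.737 at margin 2 and no true difference, against 0.946 with all 40.

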### **Statistical Procedures:**

We will enroll 80 children (40 in each group) ages 8 to 18 years. We based our sample size on the ability to demonstrate non-inferiority between the IN and IV ketorolac groups' ability to reduce pain. It has been shown that a reduction of 2 on the FPS-R score is the minimum clinically significant difference in pain in children. Therefore, our predetermined margin of non-inferiority is 2. In order to be conservative for the sample size calculation, we based the calculation on a margin of 10% less than our predetermined margin of non-inferiority of 2. The resulting sample size of 80 children, therefore, is based on a margin of 1.8 on the FPS-R pain scale. Using a standard deviation of 2.725 (again, selected using conservative assumptions), a sample size of 40 patients per group provides 90% power to detect non-inferiority using a one-sided two sample t-test with an alpha of 0.05.

We will conduct an intention to treat analysis for all enrolled randomized subjects. We will conduct a one-sided t-test to evaluate the difference between the mean decreases in pain score of the two study groups (primary outcome). The difference between groups, with its 95% CI, will be compared to the pre-determined non-inferiority margin (i.e. 2/10) to establish whether IN ketorolac is noninferior to IV ketorolac. For our secondary outcome (time to clinically significant reduction in pain), we will also compare groups using a two-sample one-

sided t-test. Similar to the analysis for the primary outcome, the difference between groups in the time to clinically significant reduction in pain, with its 95% CI, will be compared to the pre-determined non-inferiority margin of 10 minutes. A Kaplan-Meier distribution analysis will also be used to compare the time to meaningful pain relief in the two treatment groups. For other secondary outcomes, we will compare groups using standard bivariate analyses for categorical and continuous variables and a table describing adverse events by treatment will be reported.

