### **Study Design:**

We will conduct a prospective, double-blinded, randomized, non-inferiority, parallel 1:1 clinical trial of 80 children in a single urban pediatric ED. We will block randomize patients to receive either IN ketorolac (1 mg/kg) and an IV placebo (study group A), or IV ketorolac (0.5 mg/kg, maximum single dose of 30 mg) and an IN placebo (study group B). The volume of the IN placebo will be the same volume the patient would have received if they were receiving IN ketorolac; similarly, the volume of IV placebo will be the same volume the patient would have received if they were receiving IV ketorolac. Normal saline will be used as the placebo for both IN and IV administration. IN administration will be performed in a standardized fashion using a mucosal atomization device (MAD), which is a small plastic device that attaches to the end of a syringe.(47) The MAD converts any solution that is expressed from the syringe through the MAD into an atomized spray that is more readily absorbed and easier to deliver than if the solution was given as drops. All patients will receive an IV line to receive IV fluids as is typical in our ED.

The permuted, block randomization scheme will be predetermined by a third-party uninvolved with any study procedures (KB) using an online randomization program. Study group assignment will be concealed in sequentially-numbered sealed opaque envelopes which will not be opened until a patient has been enrolled. The members of the study team performing the pain assessments, those conducting the 24-hour follow up call, and the patient, will all be blinded to the study group assignment.

The chosen dosage and maximum dose of IV ketorolac are the standard of care for children.(48- 50) The maximum single dose of ketorolac which has been administered by the IN route is 30 mg; this is the maximum single dose of IV ketorolac, as well as the maximum dose of IN ketorolac that has been studied in both adults and children.(3,51) This practice is also consistent with the dosing of other IN sedatives and analgesics, in which the maximum single dose given by the IN route is the same as the as that given by the IV route.(12) The dosage of 1 mg/kg for IN ketorolac was selected based on rationale as explained as follows:

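### Non-inferiority is to be judged on intention to treat alone, with no per-protocol analysis to show whether failed IV or nasal doses have influenced the result

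*Combined protocol and SAP*

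**What the plan says.** Under Statistical Procedures the only population named is intention to treat: "We will conduct an intention to treat analysis for all enrolled randomized subjects". The primary comparison is the mean FPS-R decrease at 60 minutes. For the margin, the section states that "our predetermined margin of non-inferiority is 2". The sample size "is based on a margin of 1.8 on the FPS-R pain scale".

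Under Study Design, each child receives one active and one placebo product. Group A has nasal ketorolac with IV saline, and group B has IV ketorolac with nasal saline. On allocation: "Study group assignment will be concealed in sequentially-numbered sealed opaque envelopes which will not be opened until a patient has been enrolled". On access: "All patients will receive an IV line to receive IV fluids as is typical in our ED". The section does not say whether the line is in place before the envelope is opened.

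Study Subjects requires that the child need an IV medication, and excludes nasal obstruction that cannot be cleared. Study Procedures has the administration time recorded on the Data Collection Form, but does not mention whether each product was given in full. No section says how a failed or partial dose is to be analysed.

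**The concern.** In a superiority trial, children who miss their assigned active drug usually dilute the difference, so intention to treat is the cautious choice. In a non-inferiority trial the same dilution can help the claim, so intention to treat should not stand without a check.

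The double-dummy design makes the effect depend on which product fails:

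- **IV dose fails, group B.** The child has had only nasal saline but is analysed as IV ketorolac. The IV arm's mean decrease falls and IN looks better than it is.
- **IV dose fails, group A.** The child loses saline only, so nothing changes.
- **Nasal dose fails, group A.** The child has had only IV saline but is analysed as IN ketorolac. IN looks worse than it is.
- **Nasal dose fails, group B.** The child loses saline only, so nothing changes.

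A single intention-to-treat estimate mixes the first and third effects. A reader who saw non-inferiority declared could not tell whether untreated controls had contributed.

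**Working it through.** **Inputs from Statistical Procedures.** SD 2.725, 40 children per group, analysis margin 2, sample-size margin 1.8, one-sided alpha 0.05. The section also compares a 95% CI with the margin. If that interval is two-sided, the effective one-sided level is 0.025, so both levels are shown.

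**1. Reproduce the plan's figure.** The plan states that "a sample size of 40 patients per group provides 90% power to detect non-inferiority", "using a one-sided two sample t-test with an alpha of 0.05".

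SE = 2.725 × √(2/40) = 0.609, with 78 degrees of freedom. Taking a true difference of 0 (implied, not stated), the noncentrality is 1.8 / 0.609 = 2.95, and power from the noncentral t is 90.0%. The stated figure is reproduced.

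**2. Express the bias.** Let f be the fraction of the IV arm who receive no active drug, and e the benefit of ketorolac over saline at 60 minutes in FPS-R points. Let g and h be the corresponding fraction and benefit for failed nasal doses in the IN arm. The expected intention-to-treat deficit of IN then changes from D to

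D − f·e + g·h.

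The net shift towards non-inferiority is f·e − g·h. It is zero if the two products fail equally often with equal benefit. None of f, e, g and h is given in the documents.

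**3. Size of the IV side alone (g = 0, no effective rescue before 60 minutes).** Set the true deficit among dosed children at the margin, D = 2, so that a declaration of non-inferiority is an error. The error rate is the probability that a noncentral t with 78 degrees of freedom and noncentrality f·e / 0.609 exceeds its critical value (1.665 at one-sided 0.05, 1.991 at 0.025). With e = 2 assumed:

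| IV-arm children undosed | Shift f·e | Noncentrality | One-sided 0.05 | One-sided 0.025 |
|---|---|---|---|---|
| 0 of 40 | 0 | 0 | 5.0% | 2.5% |
| 1 of 40 | 0.05 | 0.082 | 5.9% | 3.0% |
| 2 of 40 | 0.10 | 0.164 | 6.9% | 3.6% |
| 4 of 40 | 0.20 | 0.328 | 9.4% | 5.1% |

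The benefit matters as much as the failure count. One undosed child with e = 1 (shift 0.025) gives 5.4% at one-sided 0.05. Four undosed children with e = 3 (shift 0.30) give 12.4%, but that assumes a benefit larger than the margin. Allowing for the extra IV-arm variance from mixing dosed and undosed children, f(1 − f)e², changes little: with a normal approximation, 9.3% at a shift of 0.20 and 12.2% at 0.30.

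**4. Precision of a per-protocol set.** Suppose four IV-arm children are excluded and none from the IN arm. SE = 2.725 × √(1/36 + 1/40) = 0.626, against 0.609. Power of that analysis on its own, at one-sided 0.05 and a true difference of 0, is 93.6% against 94.6% for margin 2, and 88.6% against 90.0% for margin 1.8. If four are excluded from each arm, SE = 2.725 × √(2/36) = 0.642.

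**The case against.** The strongest case against has four parts.

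**Envelope timing.** A reader might infer that the plan has envelopes opened before IV access. The text does not say so. It sets an earliest opening time, as a concealment safeguard, and separately states that every child will have a line. Local practice may well place the line first. This objection stands: the timing is unstated, which is not an error in the plan.

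**Direction.** A reader might infer that dosing failures favour non-inferiority. That is true only of failed IV doses. Refused or expelled nasal doses act against non-inferiority, and nothing in the documents shows which is more frequent. This also stands.

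**Whether the affected child exists as described.** The bias needs a group B child with no IV drug, a 60-minute score and no effective rescue before it. Under Potential Risks, additional analgesics may be given at any time, and a child left on saline is a likely candidate. Effective rescue would shrink or cancel the shift. If study drug is never given, it is also unclear when the 60-minute clock starts. These points limit the size of the effect. They do not remove the need for a check, since partial doses and late or ineffective rescue remain possible.

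**Setting.** This is a single supervised dose in an emergency department, so non-receipt may be rare and the two analyses may nearly coincide. That is plausible, but it can be shown only if dose completeness is recorded and the second analysis is run. A per-protocol set also breaks randomisation and carries its own selection bias, which is a reason to make it supportive and not a replacement.

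**Conclusion.** The gap is real but limited. A non-inferiority claim rests on one analysis set, and no planned analysis would reveal whether non-receipt of the assigned active product influenced it. The documents support neither a statement that the result will be biased towards non-inferiority nor one about its net size.

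As an assumed range, with a 2-point benefit over saline, no effective rescue, no nasal failures and 1 to 4 of 40 IV-arm children undosed, the false non-inferiority rate at a true deficit of 2 is about 5.9% to 9.4% instead of 5%. If a two-sided 95% interval decides, 2 to 4 undosed children give about 3.6% to 5.1% instead of 2.5%. With a single failure the effect is small. With four it roughly doubles the error rate at either level. Any nasal failures or effective rescue would reduce these figures and could reverse the sign.

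**What to change.** Keep intention to treat as primary. In Statistical Procedures, add a supportive per-protocol analysis of the 60-minute FPS-R decrease:

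- Include children who met eligibility and received both assigned products in full, with membership fixed before allocation is unlocked.
- State how children rescued before 60 minutes are handled in this set.
- Report its interval beside the intention-to-treat interval, both against the margin of 2, and describe a non-inferiority conclusion as not robust if they disagree. Requiring both sets to succeed would be stricter; that is a debatable trade-off and is not proposed here.

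On the Data Collection Form, record separately for the IN and IV products whether the full dose was given. A note of visible nasal loss would help, because a yes/no entry for dose given would miss a dose that was delivered and then expelled.

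As a clarification in Study Design, state that the envelope is opened once IV access is confirmed. If enrolment has finished, this no longer applies, but the per-protocol analysis can still be run where dose records allow. It should be labelled post hoc if membership was not fixed before unlocking.

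The cost is a short addition to Statistical Procedures, a sentence in Study Design, two form entries and one table. The per-protocol set will be slightly smaller, with a slightly wider interval and some selection bias of its own.
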